## **11.2. General Statistical Methods**

All statistical analyses will be performed using the SAS System software, version 9.2 or later (Copyright© 2000 SAS Institute Inc., SAS Campus Drive, Cary, North Carolina 27513, USA. All rights reserved).

All statistical analyses will be conducted according to applicable Standard Operating Procedures, Work Instructions, and the study-specific SAP.

### **11.2.1. Analysis Sets**

The primary endpoint and additional measurements will be analyzed on an ITT and an implanted basis. For ITT analyses, all subjects who sign the IRB/HREC-approved study ICF (see Section 10.3) and are enrolled in the trial will be included in the analysis, whether or not a study valve was implanted. For implanted analyses, ITT subjects who had the study valve implanted will be included in the analysis.

For the Main Cohort, the primary endpoint will be analyzed for the ITT and implanted analysis sets. The primary analysis for the primary endpoints will be based on the ITT analysis set.

### **11.2.2. Control of Systematic Error/Bias**

All subjects who have met the inclusion/exclusion criteria, received a positive recommendation from the CRC, and signed the ICF will be eligible for enrollment in the study. The center heart team's assessment of TTE measurements before device placement will contribute to the determination of subject eligibility for the study.

To control for inter-observer variability, data from independent core laboratories (see Section 13.3) will be used for analysis. These include an echocardiography core laboratory, a CT and procedural angiography core laboratory to assess all CT and procedural angiography data using standard techniques, and an electrocardiography core laboratory to independently analyze protocol-required 12-lead ECGs performed for each subject. Clinical endpoints will also be adjudicated by an independent CEC (Section 21.1.1).

### **11.2.3. Reporting Events**

For all subjects, all events that occur from the time of enrollment will be reported. For time based clinical events, the cut-off for events for 30-day endpoints will be 30 days, for 1-year endpoints it will be 365 days, and for 2–10-year endpoints it will be 365 days times the number of years. For events at discharge or 7 days post-procedure, the cut-off for events will be the earlier of the date of discharge or 7 days post-procedure for each subject.

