## 9. Subject Accountability

### 9.1. *Point of Enrollment*

Subjects who are confirmed eligible for the study by the CRC (see Section 21.2) and who provided written informed consent are considered enrolled in the study as soon as an attempt is made to insert the LOTUS *Edge* Valve System into the subject's femoral artery.

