**Table 10.1-1: Study Event Schedule**

Assessment	Screening a	Baseline	Procedure	Within 1 Day Post-procedure	Prior to Discharge or 7 Days Post-Procedure	30 Days b (±7 Days) Office Visit	12 Months b (±30 Days) Office Visit	24–60 Months b [Annual] (±45 Days) Office Visit	84 and 120 Months b (±60 Days) Office/In person Visit	72, 96, and 108 Months b (±60 Days) Telephone
------------	------------------------	----------	-----------	-----------------------------	---	---	--	--	--	--

Core Laboratory with the screening CT angiogram of the aortic structure. An iliofemoral invasive angiogram may be substituted for the iliofemoral CT angiogram.

- o: Includes the Kansas City Cardiomyopathy and SF-12 QOL questionnaires. Baseline QOLs should be performed within 30 days prior to the index procedure.
- p: QOL survey at 60 months.
- q: Procedural cine-angiogram including the baseline images of the aortic complex and the final post-deployment aortogram of the ascending aorta must be performed and sent to the CT/X-Ray Core Laboratory for analysis.
- r: AEs and ADEs will be monitored and collected from the time of enrollment through 12-month follow-up. For subjects who do not receive the study device, AEs will be monitored through 12-month follow-up.
- s: Information on device deficiencies for the test device(s) will be monitored and reported to Boston Scientific. Information on all SAEs, SADEs, UADEs, and CEC events will be monitored and reported to Boston Scientific for enrolled subjects from the time of enrollment through 5 years. After 5 years, serious adverse event assessment (includes SAE, SADE, UADE, and relevant VARC events to be adjudicated by the CEC [see *Note 4* below]) for test device(s) and device deficiencies assessment for test device(s) with associated treatment will be monitored and reported to Boston Scientific for enrolled subjects through termination of the study. For subjects who do not receive a study device, the aforementioned events will be monitored through 1-year post-index procedure. Please refer to Section 6.2.2 for a list of CEC events and Table 25.2-1 for definitions of these events, which specify data required for CEC adjudication. Complaint reporting of any device deficiencies for any commercially available products used should be carried out using the manufacturer’s processes.  

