### 10.7. *Index Procedure*

The preparation of the subject for the percutaneous procedure will be performed following standard techniques. Transfemoral access must be attempted for all subjects (assessment of the iliofemoral system prior to subject enrollment must indicate that transfemoral access is considered appropriate). If the transfemoral approach is unsuccessful, the operator will decide the best alternative approach to treat the subject.

**Note 1:** Additional concomitant procedures, including percutaneous coronary intervention, are not allowed during the index procedure.

**Note 2:** The subject should undergo the index procedure within 30 days after signing the study Informed Consent Form.

The large Lotus Introducer Set (Section 5.1.3) or, when available, the iSleeve Introducer Set (Section 5.1.3) is prepared and introduced in the patient's femoral artery, as described in the iSleeve/Lotus Introducer IFUs. A balloon valvuloplasty on the existing valve following standard techniques may be performed with an appropriately sized valvuloplasty balloon (avoid oversizing) before implantation of the LOTUS *Edge* valve. Careful attention should be paid to the position of the guidewire throughout the BAV procedure. Prior to introduction of the LOTUS *Edge* Valve System, the subject's hemodynamic status and heart rhythm must be assessed and documented (12-lead ECG is not required). Information on the BAV, including number of inflations, should be documented in the source data and will be captured in the eCRFs.

**Note 3:** It is recommended that predilatation be performed unless there is minimal calcification of the annulus and leaflets; BAV must be performed in subjects in the Bicuspid Nested Registry cohort.

**Note 4:** If the subject becomes hemodynamically unstable after the valvuloplasty for reasons unrelated to the aortic valve annulus and/or leaflets, the LOTUS *Edge* valve implantation should be interrupted until the subject is stable.

The LOTUS *Edge* valve implantation procedure requires two operators: First and Second Operators. Both operators must comply with the IFU and must be adequately trained and

certified by BSC personnel before performing the procedure (see Section 16.4.216.4.2 for additional information on training). Guidelines provided by the Sponsor for valve size selection should be followed.

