- Date of procedure
- Device size (23mm, 25mm, or 27mm) and model
- Time of puncture (at site of TAVR sheath) and time of vascular closure for TAVR sheath (iSleeve/Lotus Introducer insertion and removal time)
- Descriptive information on balloon valvuloplasty, if performed (e.g., size of balloon, number of balloon inflations)
- Adjunctive procedures performed during implant procedure
- LOTUS *Edge* Valve System catheter insertion and removal time
- Descriptive information on LOTUS *Edge* valve implantation procedure and information on valve repositioning or retrieval (if performed)
- Adverse event (AE) assessment and associated treatment (including AE, serious adverse event [SAE], serious adverse device effect [SADE], unanticipated adverse device effect [UADE], adverse device effect [ADE] and Clinical Events Committee [CEC] events; see Section 19).
- Device deficiencies assessment for the LOTUS *Edge* Valve System

**Note 5:** All LOTUS *Edge* valve implantation procedures will be performed with the support/presence of trained BSC personnel (see Section 16.4.1).

**Note 6:** In countries where the introducer sets are approved, a device deficiency should be reported as a complaint.

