## 19. Safety Reporting

### 19.1. Reportable Events by Investigational Center to Boston Scientific

It is the responsibility of the investigator to assess and report to BSC any event that occurs in any of the following categories; reporting requirements are described below in **Table 19.4-1**.

- All serious adverse events
- All device-related adverse events
- All study procedure-related adverse events
- All investigational device deficiencies
- Unanticipated adverse device effects/unanticipated serious adverse device effects
- New findings/updates in relation to already reported events

When possible, the medical diagnosis should be reported as the Event Term instead of individual symptoms.

If it is unclear whether or not an event fits one of the above categories, or if the event cannot be isolated from the device or procedure, it should be submitted as an adverse event and/or device deficiency.

Any adverse event required by the protocol, experienced by the study subject after informed consent and once considered enrolled in the study (as defined in Section 9.1), whether during or subsequent to the procedure, must be recorded in the eCRF.

Underlying diseases are not reported as AEs unless there is an increase in severity or frequency during the course of the investigation. Death should not be recorded as an AE but should only be reflected as an outcome of ONE (1) specific SAE (see **Table 19.2-1** for AE definitions).

In-patient hospitalization is defined as the subject being admitted to the hospital, with the following exceptions.

- A hospitalization that is uncomplicated and elective/planned (i.e., planned prior to enrollment) does not have to be reported as an SAE.
- If complications or AEs occur during an elective/planned (i.e., planned prior to enrollment) hospitalization after enrollment, the complications and AEs must be reported as AEs or SAEs if they meet the protocol-specified definitions.

Event reporting (eCRF data entry) is required beginning from the time an attempt is made to insert the LOTUS *Edge* Valve System into the subject's femoral artery.

Refer to Section 18 for the known risks associated with the study devices.

Based on the VARC recommendations and definitions, the adverse events and/or safety endpoints requiring adjudication by the CEC include the following.

- Mortality: all-cause, cardiovascular, and non-cardiovascular
- Stroke: disabling and non-disabling

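### In enrolled subjects, event reporting opens at the LOTUS Edge insertion attempt, so complications that begin and qualify during earlier introducer placement or predilatation may not be captured

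*Combined protocol and SAP*

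**What the plan says.** The start of the event window is stated several times, consistently:

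- Section 9.1: eligible, consented subjects "are considered enrolled in the study as soon as an attempt is made to insert the" LOTUS Edge Valve System into the femoral artery.
- Section 11.2.3: "For all subjects, all events that occur from the time of enrollment will be reported".
- Section 19.1: "Event reporting (eCRF data entry) is required beginning from the time an attempt is made to insert the LOTUS" Edge system. The same section limits recorded adverse events to those arising after consent and once the subject is enrolled.
- Table 10.1-1, footnote r: "AEs and ADEs will be monitored and collected from the time of enrollment through 12-month follow-up". Footnote s opens SAE and CEC-event collection at the same moment.

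Section 10.7 gives the order of the procedure. The introducer goes into the femoral artery first. Then "A balloon valvuloplasty on the existing valve following standard techniques may be performed with an appropriately sized valvuloplasty balloon", before the study valve is implanted. Predilatation is recommended unless calcification is minimal, and it is compulsory in the Bicuspid Nested Registry. Only then is the LOTUS Edge catheter passed into the introducer. Sections 5.1 and 5.1.3 treat the introducer as an accessory to a system made up of the valve and its delivery catheter. Placing the introducer is therefore not the insertion attempt.

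Among the data to be captured during the procedure, Section 10.7 lists "Time of puncture (at site of TAVR sheath) and time of vascular closure for TAVR sheath" and an assessment of adverse and CEC events.

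**The concern.** The study objective (Section 6.1) is to evaluate LOTUS Edge when used with the named introducer sets. The stated window nevertheless opens after the introducer is in place and after any valvuloplasty. Note 4 of Section 10.7 foresees a subject who becomes hemodynamically unstable after valvuloplasty and whose implantation is interrupted until the subject is stable. If the procedure then resumes, that subject is enrolled and enters the ITT set, with a complication that began before time zero.

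Any loss runs in one direction: it can only lower observed rates. Sites could also record the same injury differently, and the protocol gives the CEC no rule on which clock governs. The point concerns events in analysed subjects. Subjects whose procedure stops before the insertion attempt are a separate matter.

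**Working it through.** **1. The passages side by side**

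| Window opens at the insertion attempt | Text that points to the whole procedure |
|---|---|
| 9.1 with 11.2.3 | 10.7: adverse and CEC events assessed during the procedure |
| 19.1: recorded events limited to enrolled subjects; start of eCRF entry | 19.1: all events related to the study procedure are listed as reportable |
| Table 10.1-1, footnotes r and s | Table 10.1-1: event assessments marked in the Procedure column |
| | Table 25.2-1: procedure-related complications include those of vascular access; major vascular complications include access-related injury |

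The left column sets an explicit start time. The right column describes scope and does not say that an event which begins and is recognised before the attempt must be entered.

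**2. What could be lost, and what is not**

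- Could be lost: events that both begin and meet their definition between puncture and the insertion attempt.
- Still counted: closure problems (closure comes last in Section 10.7), and bleeding, ischemia or neurological deficit that appears after the attempt.
- Still counted: new pacemakers, which Table 25.2-1 defines as implanted after the index procedure.
- Not at risk: deaths. An enrolled subject cannot have died before enrollment, so only a stroke could drop out of the primary composite.

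**3. The plan's own figures**

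Inputs from Section 11.1.1.2: performance goal p0 = 0.152, expected rate p1 = 0.111, one-sided alpha 0.025, n = 675.

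- Null standard error: √(0.152 × 0.848 / 675) = 0.01382. Standard error at p1: √(0.111 × 0.889 / 675) = 0.01209.
- Power: Φ[(0.041 − 1.96 × 0.01382) / 0.01209] = Φ(1.151) = 87.5%, as stated.
- Enrollment: 675 / 0.97 = 696, as stated.
- Pass threshold: 0.152 − 1.96 × 0.01382 = 0.1249; × 675 = 84.3, so the test passes with 84 events or fewer.

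**4. Sensitivity of the primary test**

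Suppose the true whole-procedure rate is 15.2% and k strokes among 675 go uncounted. The pass probability is then the exact binomial P(X ≤ 84) at rate 0.152 − k/675.

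- k = 0: 2.4%.
- k = 1: rate 0.1505, giving 3.0%.
- k = 3.4 (0.5 percentage points): rate 0.147, giving 5.2%.

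The value of k is an assumption; the documents give no rate of stroke before the insertion attempt.

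**5. Background frequency of the procedural endpoints**

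Table 4.1-11 gives 30-day Lotus rates of 4.7% (28/601) for access-site major vascular complications and 2.5% (15/601) for tamponade. If 10% to 30% of the access-site events preceded valve insertion (an assumption with no source in the documents), 0.47 to 1.41 points would be exposed, or about 3 to 10 of 696 subjects. This is an illustration, not an estimate.

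**The case against.** The strongest reply is that the plan already reaches the whole procedure. Section 19.1 lists all procedure-related adverse events as reportable and asks for submission of any event that cannot be separated from the device or procedure. Section 10.7 and the Procedure column of Table 10.1-1 require assessment on the day. The cut-offs in Section 11.2.3 are in days, and the AE page is described as holding a date, with no onset time mentioned. A same-day complication would therefore carry the enrollment date, and nothing tells the analyst to remove it. This stands to a degree: loss is more likely at site entry than in the analysis, and a conscientious site may enter the event anyway. It does not settle which text governs, because the explicit start rule appears in four places.

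A reader might infer that all complications of access and predilatation go uncounted. The documents do not support that. A major vascular complication often depends on a consequence such as bleeding or ischemia, and these consequences can appear after the attempt. A reader might also infer that pacemaker rates are biased low. They are not, because pacemakers implanted after the procedure fall inside the window, whenever the conduction disturbance was first seen.

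Finally, a reader might infer that the type I error of the primary test is materially inflated, to 5% or so. That needs more than three strokes with onset before insertion. Table 25.2-1 dates a neurological event after emergence from anesthesia, although its stroke definition does not repeat this. The calculation also presumes that the studies behind the performance goal counted from puncture, which cannot be checked from these documents.

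**Conclusion.** The concern holds in a limited form. In enrolled subjects the written rule opens reporting after introducer placement and predilatation. Events that begin and qualify before the insertion attempt may therefore be missed, and this conflicts with other text in the same protocol. The exposure lies mainly in the vascular, bleeding and tamponade endpoints, which are descriptive and carry no hypothesis (Section 11.3.1).

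The size of the undercount cannot be derived from the documents. The Table 4.1-11 rates come from the first-generation Lotus valve in extreme- or high-risk subjects, counted from randomization, so they show only that such events are not rare. The effect on the primary test is probably small: 2.4% to 3.0% for one uncounted stroke, on the assumption that such a stroke occurs at all. The sample size and power figures are not in error. This is a cheap improvement, not a threat to the design.

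**What to change.** Keep the point of enrollment in Section 9.1 and the ITT set as they are. In Sections 11.2.3 and 19.1 and in Table 10.1-1 footnotes r and s, state that for every enrolled subject events are reported and counted from the first vascular puncture of the index procedure. The reference is the TAVR-sheath puncture time already collected under Section 10.7. Repeat the rule in the eCRF completion guidance and the CEC charter, so that sites and adjudicators use the same clock.

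The cost is wording and site guidance; no new data field is needed. The downside is that observed rates may become slightly less favourable.

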## **11.3. Data Analyses**

Baseline and outcome variables will be summarized using descriptive statistics for continuous variables (mean, standard deviation, number of observations, minimum and

maximum) and discrete variables (percentage and count/sample). See Section 11.1 for a discussion on analysis of the primary endpoint and additional measurements.

### **11.3.1. Other Measurements**

Other measurements not driven by statistical hypotheses are listed in Section 6.2.2.

### **11.3.2. Interim Analyses**

No formal interim analyses are planned for the purpose of stopping this trial early for effectiveness or futility. Administrative analyses for regulatory agency review may be performed.

### **11.3.3. Justification of Pooling**

All analyses will be performed using data pooled across clinical centers. An assessment of the poolability of subjects across centers will be made by fitting a logistic regression model with the primary composite endpoint of all death and all stroke and with the center as the main effect. If the  $P$  value for the coefficient for the center is  $\geq 0.1$ , the data can be pooled across centers. In the analysis to justify pooling across centers, the centers with fewer than 10 subjects enrolled will be combined into “virtual centers” based on geographic region so that “virtual centers” have  $\geq 10$  subjects, but no more than the largest enrolling center.

### **11.3.4. Multivariable Analyses**

Univariate and multivariate analyses will be performed to assess the effect of potential predictors on the primary endpoint as described in the SAP.

### **11.3.5. Changes to Planned Analyses**

Any changes to the planned statistical analyses made prior to performing the analyses will be documented in an amended SAP approved before performing the analyses. Changes from the planned statistical methods after performing the analyses will be documented in the clinical study report along with a reason for the deviation.

## **12. Health Economics Outcomes**

A formal health economics analysis may be completed as part of this trial, provided meaningful clinical results are obtained. Quality of life will be evaluated by the Kansas City Cardiomyopathy and SF-12 questionnaires at baseline, 1 month, 1 year, and 5 years. These inputs may be used in any health economics analysis performed.

## **13. Data Management**

### **13.1. *Data Collection, Processing, and Review***

Subject data will be recorded in a limited access secure electronic data capture (EDC) system. Only personnel trained and authorized will have access to the system.

The clinical database will reside on a production server hosted by Medidata EDC System (New York, NY, USA). All changes made to the clinical data will be captured in an electronic audit trail and made available for review by BSC or its representative. The associated RAVE software and database have been designed to meet regulatory compliance for deployment as part of a validated system compliant with laws and regulations applicable to the conduct of clinical studies pertaining to the use of electronic records and signatures. Database backups are performed regularly.

The Investigator provides his/her electronic signature on the appropriate eCRFs in compliance with local regulations. A written signature on printouts of the eCRFs must also be provided if required by local regulation. Changes to data previously submitted to the Sponsor require a new electronic signature by the Investigator acknowledging and approving the changes.

Visual and/or electronic data review will be performed to identify possible data discrepancies. Manual and/or automatic queries will be created in the EDC system and will be issued to the center for appropriate response. Center staff will be responsible for resolving all queries in the database.

### **13.2. *Data Retention***

The Principal Investigator or his/her designee or investigational center will maintain all essential study documents and source documentation that support the data collected on the study subjects in compliance with applicable regulatory requirements. Documents must be retained for at least 2 years after the last approval of a marketing application or until at least 2 years have elapsed since the formal discontinuation of the clinical investigation of the product. These documents will be retained for a longer period of time by agreement with BSC or in compliance with other local regulations. It is BSC's responsibility to inform the Investigator when these documents no longer need to be maintained.

The Principal Investigator or his/her designee will take measures to ensure that these essential documents are not accidentally damaged or destroyed. If for any reason the Principal Investigator or his/her designee withdraws responsibility for maintaining these essential documents, custody must be transferred to an individual who will assume responsibility and BSC must receive written notification of this custodial change. Centers are required to inform BSC in writing where paper or electronic files are maintained in case files are stored off site and are not readily available.

